9.3.2 Other risk adjustment

The following Cox proportional hazards time to event regression model describes the method of another risk adjustment:

$$\lambda(tX_j) = \lambda_0(t) * \exp(\beta_1 X_{j1} + \beta_2 X_{j2} + \dots + \beta_m X_{jm})$$

This expression gives the hazard rate at time t for person j

- $\lambda(tX_j)$ is the hazard for outcome at time t for person j
- where \exp is a mathematical constant, Euler's number ($e = 2,71828$)
- X_1, \dots, X_m are the values of exposure variables and covariates
- β_1, \dots, β_m are estimated regression coefficients that indicate the importance of exposure variables and covariates.
- $\lambda_0(t)$ is the baseline hazard indicating hazard for the outcome if all exposure variables are zero (similar meaning "intercept").

Following covariates will be used in the Cox proportional hazards time to event regression:

- **Gender** (sex – male, female) will be assessed via indicated sex in the social insurance register

¹¹ Ray et al., 2016

- **Age** will be assessed using national insurance data by date of birth and calculated based on the 'index treatment' (the date of first study medication claim between 1st January 2012 and 31st December 2017).
- **Charlson Comorbidity Index (CCI)** will base on the the modified CCI according to Quan (2005) and Quan (2011). Using modified CCI is preferable because it was validated by ICD-10 while, for example, the Romano-CCI was validated using ICD-9¹². The modified CCI predicts the one-year mortality for a patient who may have a range of comorbid conditions (e.g. AIDS, or cancer) with a total of 16 conditions¹³. Each condition is assigned a score between 0 (no risk) and 6 (high risk), depending on the risk of dying associated with conditions. Age and gender are defined as hazard ratios. The scores are summed up to provide a total score to predict mortality. CCI will be added as a covariate in the Cox regression model (Table 9-4).
- **Duration of the opioid /non-opioid treatment** will be used as a one of the predictors of opioid treatment in be added as a covariate in the Cox regression model and assessed as the difference between the last opioid or non-opioid prescription based on ATC codes and the first opioid or non-opioid prescription in months, between January 1st 2012 and December 31st 2016. The prescription will be dummy coded as 1 (prescription available) or 0 (no prescription available).
- **Quarter of index treatment:** Quarter in which index treatment was initiated, wheras Q1/2012 is quarter=1, Q2/2012 is quarter=2 and so on.
- **Propensity Score** as calculated before

¹² Yurkovich et al 2015

¹³ Quan et al 2011

Table 9-4: Charlson Comorbidity Index

Condition	Scale	Points	ICD-10-GM Code
Myocardial infarction	No	0	
	yes	1	I21*-I22*, I25.2
Congestive Heart Failure	No	0	
	yes	1	I50*
Peripheral vascular disease	No	0	
	yes	1	I73*, I74.2, I74.3, I74.4, I71.3, I71.5, I71.4, I71.6
Cerebrovascular accidents	No	0	
	yes	1	I60*-I69*
Dementia	No	0	
	yes	1	F00*-F03*, F05.1
Chronic obstructive pulmonary disease	No	0	
	yes	1	J44*
Rheumatic disease	No	0	
	yes	1	M05*, M06*, M31.5, M32-M34, M35.3, M45*,
Peptic ulcer disease	No	0	
	yes	1	K25*, K26*, K27*, K28*
Liver disease	No	0	
	Mild	1	K70.1-K70.3, K70.9, K71-K71.0, K71.2-K71.8, K73*, K74.0, K74.2, K74.6, K74.3, K74.4, K74.5
	Severe	3	K70.4, K71.1, K72*, K76.3
Diabetes mellitus	No	0	
	Un-complicated	1	E10.9*, E11.9*, E13.9*, E14.9*, E10.1*, E11.1*, E13.1*, E14.1*
	Complicated / end organ damage	2	E10.2*, E11.2*, E13.2*, E14.2* E10.3*, E11.3*, E13.3*, E14.3* E10.4*, E11.4*, E13.4*, E14.4*, E10.5*, E11.5*, E13.5*, E14.5*
Hemiplegia	No	0	
	yes	2	G81*
Kidney diseases	No	0	
	yes	2	N17*-N19*
Cancer	No	0	
	Solid	2	C00*-C76*, C80*, C81*, C82*, C83*, C84*, C88.3, C88.7, C88.9, C96*, C90.1, C91*-C95*, C81*, C82*, C83*, C84*, C85*, C86*, C88*
	Metastatic	6	C77*, C78*, C79*, C80*
AIDS / HIV	No	0	
	yes	6	B20* - B24*
Demographics as risk factors			
		Hazard Ratio	
age (> 65 years)		4,40	
gender (male)		1,28	

The Cox proportional hazards model will use treatment dosage as time-varying covariates, re-calculating it annually during follow up. The model will also be adjusted for age, gender, CCI at the baseline. Covariates will not be treated as time varying variables.

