9.2.1 Study Period

Due to data protection regulations in Germany, only an extract of maximum 6 years of data coverage could be available for the research purposes: 1st January 2012 to 31st December 2017.

The **baseline period** is defined as the period prior to the date of first diagnosis of diagnoses or first opioid or non-opioid treatment initiation as described in inclusion criteria (Chapter 9.2.2.1). The baseline assessment period endures between January 01, 2012 and first study medication prescription.

Index treatment is defined as the date of first opioid or non-opioid treatment prescription between 1st January 2013 and 31st December 2017.

Exposure time is defined as time between index treatment and December 31, 2017. Considering data availability of a maximum of 6 years and prescription in a required time period of 60 months, exposure time endures maximum five years. Thus, patients can be censored at death (death date in the linked records), last known record for the patient in the German health claims database, switching of treatment groups (from opioid group to non-opioid group or vice versa), 12 months without opioid/non-opioid treatment or 31st December 2017 (end of latest data cut), whichever comes first.

[figure not shown]
The **outcomes** will be assessed between index treatment and 31.12.2017.

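### Section 9.3.2 adjusts the mortality Cox model for total treatment duration, a post-index quantity capped by survival, which biases the opioid hazard ratio whenever persistence differs between the cohorts

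*Protocol*

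**What the plan says.** The covariate list in protocol section 9.3.2 opens with "Following covariates will be used in the Cox proportional hazards time to event regression". One entry is the duration of opioid or non-opioid treatment, "assessed as the difference between the last opioid or non-opioid prescription based on ATC codes and the first opioid or non-opioid prescription in months". Section 9.4.1 defines duration in the same way. The list also contains index quarter ("Quarter in which index treatment was initiated") and the propensity score.

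The end of 9.3.2 says the model "will use treatment dosage as time-varying covariates, re-calculating it annually during follow up", and then "Covariates will not be treated as time varying variables". Read together, dosage is the only covariate that changes with time, and duration is one fixed number per patient.

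Section 9.2.1 sets time zero: "Index treatment is defined as the date of first opioid or non-opioid treatment prescription between 1st January 2013 and 31st December 2017". Section 9.4.2.1 makes death from any cause the primary endpoint. Under 9.1 and 9.2.1, follow-up ends at death, a change of treatment group, 12 months without treatment, the last record or the end of 2017.

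**The concern.** A Cox covariate held fixed from time zero has to be known at time zero. Total duration is not: it is complete only when treatment ends, and death ends treatment. A short duration is therefore partly a consequence of the outcome, and the model will credit long duration with preventing death even if it has no effect.

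This matters beyond the duration coefficient. Opioids are compared with a mixture of NSAIDs, metamizole, antidepressants and anticonvulsants, and nothing in the protocol suggests that patients stay equally long on both sides. If they do not, the false duration effect passes into the treatment hazard ratio, which answers the main question in section 8.1. The result would then partly reflect which cohort persists longer. Propensity matching (9.3.1) cannot prevent this, because duration arises after matching. Section 9.10.1.4 relies on the size of the data to control confounding, but size only makes a biased estimate more precise.

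**Working it through.** The protocol states no hazard ratio, event count or cohort size on this point, so there is no figure to reproduce. The check is structural first, then by simulation.

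**1. Why duration looks protective.** Let D be last minus first prescription and A the cohort (1 = opioid). A death at time t contributes exp(β_A·A + β_D·D) for the patient who died, divided by the sum of the same term over everyone still at risk. Take t = 24 months. Anyone still followed has not gone 12 months untreated, so D is at least 24 − 12 = 12 months. The patient who dies has D between 12 and 24. The others have D between 12 and 60, the maximum in section 9.1. The death always sits at the low end, so β_D is negative without any true effect.

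**2. How it reaches the treatment effect.** With no true effect, the model must offset the false duration term: roughly β_A ≈ −β_D × (mean D, opioid − mean D, non-opioid). In the simulation below with stopping rates 0.3 v 0.5, mean durations were 24.3 and 21.6 months (difference 2.7) and the false duration hazard ratio was 0.88 to 0.89 per month. So β_A ≈ 2.7 × 0.128 = 0.345 to 2.7 × 0.117 = 0.315, a hazard ratio of about 1.41 to 1.37. This ignores the spread of durations and overshoots the simulated 1.32, but it gives the right sign and order. With equal persistence the difference, and hence the bias under the null, is zero.

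**3. Simulation.**
- From the protocol: 150 deaths per 10,000 person-years (midpoint of the 100 to 200 in 9.3.1), 9 months' minimum treatment (9.4.1), the end-of-follow-up rules in 9.1 and 9.2.1, and index quarter as a covariate.
- Assumed: 8,000 per cohort; entry uniform from January 2013 to March 2017; exponential stopping and switching after 0.75 years, with switching at 0.1 per year in both cohorts; death unrelated to persistence.
- Model: cohort, duration and index quarter. There were 1,000 replicates per scenario, about 365 deaths each, and a Monte Carlo standard error of about 0.003 on the log hazard ratio.

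True hazard ratio 1.00. Values in brackets are with the cohorts swapped.

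| Stopping per year, opioid v non-opioid | No duration | Duration, 2013–2017 window | Duration, 2012–2016 window |
|---|---|---|---|
| equal | 1.00 | 1.00 | 1.00 |
| 0.38 v 0.42 | 1.00 | 1.05 (0.94) | 1.03 (0.96) |
| 0.35 v 0.45 | 1.00 | 1.15 (0.87) | 1.09 (0.92) |
| 0.3 v 0.5 | 1.00 | 1.32 (0.76) | 1.18 (0.85) |

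Two windows are shown because the protocol gives two (see the fix).

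**4. Sensitivity, 0.3 v 0.5, 2013–2017 window.**
- Switching 0 to 0.2 per year: 1.31–1.35 (0.74–0.76).
- 100 and 200 deaths per 10,000 person-years: 1.32–1.33 (0.75).
- Half-year minimum treatment with entry to June 2017: 1.31 (0.75).
- True hazard ratio 1.5: 1.48–1.50 without duration; 1.98 (1.12) with it.

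Equal stopping but switching at 0.05 v 0.2 per year gave 1.05 under the null.

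**5. Second simulation with other persistence assumptions.** 20,000 per cohort, 4 replicates, 100 or 200 deaths per 10,000 person-years, no switching, 9 months plus an exponential extra treatment time:

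| Mean extra months, opioid v non-opioid | True 1.0, with duration | True 1.5, with duration |
|---|---|---|
| 18 v 18 | 1.02–1.03 | 1.48–1.51 |
| 12 v 24 | 0.71 | 1.02–1.07 |
| 6 v 24 | 0.53–0.54 | 0.77–0.79 |
| 24 v 12 | 1.44–1.47 | 2.11–2.19 |

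Without duration the results were 1.01–1.03 and 1.46–1.53. The false duration hazard ratio was about 0.90 per month.

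**6. False-positive rate.** For 0.3 v 0.5 with a two-sided 5% Wald test (assumed; 9.7.1 states 5% only for the t and chi-squared tests), the rate was about 29%, 77% and 98% at 2,000, 8,000 and 20,000 per cohort in the 2013–2017 window. In the 2012–2016 window it was 13%, 33% and 72%. Without duration, at 8,000, it was 5%.

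**The case against.** **The model may not really contain duration.** The sentence in 9.3.2 is garbled and is followed by a 1/0 code for whether a prescription exists. The closing summary of the model names only age, gender and the Charlson index besides dosage, and the synopsis names only those three. But the shorter lists also leave out index quarter and the propensity score, which are clearly intended, so they read as summaries. The 1/0 code cannot replace the measure in months: section 9.2.2.1 requires treatment over at least three quarters, so every patient would be coded 1. At best the primary model is ambiguous. Nor is this a detail left to a statistical analysis plan, because the protocol specifies the covariate.

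**The size rests on assumed persistence.** This stands. The protocol gives no stopping rates, switching rates or cohort sizes. The false-positive rates come from the widest of the stopping contrasts in step 3, while the mildest gives 1.05 (0.94).

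**The simulated model is simpler than the planned one.** This also stands. It leaves out matching, the propensity score, age, gender, the Charlson index and annually updated dosage. Dosage is built from prescriptions and may share information with duration, so the size under the full model could differ. None of these terms changes the fact that duration is fixed after time zero and bounded by survival, so none can be assumed to remove the bias.

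**Conclusion.** The concern holds. As written, the primary mortality model conditions on future information that death itself truncates. The mechanism does not depend on the simulation assumptions; the size does. Under the null there is no bias if persistence is equal, about 5% for a small difference in stopping (0.38 v 0.42 per year), and roughly a 30% rise or a 24% fall for 0.3 v 0.5. The direction is set by which cohort stays on treatment longer. A true hazard ratio of 1.5 could appear as about 1.0 or about 2.1 under the 12 v 24 month contrasts, so the artefact can create, hide or inflate a mortality signal. Because it affects the main comparison and is avoidable, it must be fixed before analysis.

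**What to change.** - Delete duration of treatment from the Cox covariate list in 9.3.2 and report it descriptively by cohort.
- State that all Cox covariates other than dosage are fixed at baseline. Section 9.3.2 nearly says this already; one clear sentence removes the doubt. The handling of time-varying dosage is not part of this change.
- If cumulative exposure is of interest, use only the duration accrued up to time t, as a time-updated covariate in a separate, non-primary analysis. Under the null this gave treatment hazard ratios of 0.999 and 1.002 (standard error 0.004; 600 replicates of 8,000 per cohort). It was not checked under a true effect.

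Separately, reconcile the dates. Section 9.3.2 measures duration as "prescription in months, between January 1st 2012 and December 31st 2016", and the treatment definitions in 9.4.1 use the same years, while 9.1, 9.2.1, 9.2.2.1 and the duration entry in 9.4.1 use 2013–2017. Patients starting in 2017 have no defined duration under 9.3.2 and fall outside the exposure definition in 9.4.1. This conflict does not cause the bias and would remain in 9.4.1 after the deletion.

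The cost is protocol wording only: no extra data, and no objective in section 8.1 is lost.

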9.2.2 Patient Eligibility

9.2.2.1 Inclusion Criteria

For the purposes of this study, the requested extraction of the database consists of population of patients with chronic non-cancer pain corresponding to the following criteria. Inclusion and exclusion criteria are also provided in Figure 2.

Figure 2: Inclusion and exclusion criteria

Cohort A

- Patients are included in the long-term opioid group if they started an opioid-therapy between 2013 and 2017 and received consecutive prescriptions for opioid medications over a minimum of 3 quarters, over a 60-month period between January 1, 2013, and December 31, 2017. The treatment will be assessed using the ATC codes of opioid treatment N02AA01, N02AA05, N02AB03, N02AE01, N02AX02, N02AX01, N02AX06 (see also Table 9-1) reported in reimbursed medicines to patients.

- Patients are only included if they have been diagnosed in at least three quarters in the study period with one of the following diagnoses: R51, R52*, M00*-M99*, G43*-G44*, G50.0 or G50.1, F45.4*, G62*, or E10.4*-E14.4 plus G63.3. At least one diagnoses must be between 1 January 2012 and index treatment and main and secondary hospital diagnoses (*i.e. Haupt- und Nebendiagnosen*) will be used to include the patients.

Cohort B

- Patients with non-opioid pain medication are included, if they received a medication therapy with anticonvulsants (gabapentin, pregabalin, carbamazepine), antidepressants or non-opioid analgesics (NSAIDs, Metamizole) over a minimum of 3 quarters, over a 60-month period between January 1, 2013, and December 31, 2017. The non-opioid treatment will be assessed using the ATC codes (N03AX12, N03AX16, N03AF01, see also Table 9-1) of treatment reported in reimbursed medicines to patients.
- Patients are only included if they have been diagnosed in at least three quarters in 2012 with one of the following diagnoses: R51, R52*, M00*-M99*, G43*-G44*, G50.0 or G50.1, F45.4*, G62*, or E10.4*-E14.4 plus G63.3. At least one diagnoses must be between 1 January 2012 and index treatment and main and secondary hospital diagnoses (*i.e. Haupt- und Nebendiagnosen*) will be used to include the patients.

All diagnoses that lead to patient inclusion when coded between 01.01.2012 and index treatment and in at least three quarters within the study period are provided in Table 9-2 below.

Table 9-1: List of ATC codes of study opioid and non-opioids

Name	ATC Code
Study opioids	
Morphine	N02AA01
Oxycodone	N02AA05
Fentanyl	N02AB03

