Buprenorphine	N02AE01
Tramadol	N02AX02
Tilidine	N02AX01
Tapentadol	N02AX06
Study non-opioids (anticonvulsive)	
Gabapentin	N03AX12
Pregabalin	N03AX16
Carbamazepine	N03AF01
Study non-opioids (antidepressants)	
Non-selective monoamine reuptake inhibitors	N06AA*
Selective serotonin reuptake inhibitors	N06AB*
Monoamine oxidase inhibitors, non-selective	N06AF*
Monoamine oxidase A inhibitors	N06AG*
Other antidepressants	N06AX*
Study non-opioids (Nonsteroidal anti-inflammatory drugs)	
Butylpyrazolidines	M01AA*
Acetic acid derivatives and related substances	M01AB*
Oxicams	M01AC*
Propionic acid derivatives	M01AE*
Fenamates	M01AG*
Coxibs	M01AH*

Other antiinflammatory and antirheumatic agents, non-steroids	M01AX*
Study non-opioids (others)	
Metamizole	N02BB02

Table 9-2: List of included ICD-10 diagnoses for both cohorts

Name	ICD-10 Code
Diseases of the musculoskeletal system and connective tissue	M00* - M99*
Headache	R51
Pain, not elsewhere classified	R52*
Migraine	G43*
Other headache syndromes	G44*
Trigeminal neuralgia	G50.0
Atypical facial pain	G50.1
Persistent somatoform pain disorder	F45.4*
Other and unspecified polyneuropathies	G62*
Diabetes mellitus with neurological complications	E10.4-E14.4
AND	
Polyneuropathy in diseases classified elsewhere	G63.3

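### The Charlson table (Table 9-4) gives no points to E12, to C90 other than C90.1, or to C97, although the protocol's own inclusion and exclusion lists count E12.4 as complicated diabetes and C00-C97 as malignancy

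*Protocol*

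**What the plan says.** Protocol section 9.3.2 makes a modified Charlson Comorbidity Index (CCI) a covariate of the Cox model. It sums the points over conditions and fixes codes and points in Table 9-4.

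- **Diabetes, 1 point (uncomplicated):** "E10.9*, E11.9*, E13.9*, E14.9*, E10.1*, E11.1*, E13.1*, E14.1".
- **Diabetes, 2 points (complicated):** fourth digits .2 to .5 of the same categories, ending in "E10.4*, E11.4*, E13.4*, E14.4*, E10.5*, E11.5*, E13.5*, E14.5".
- **Cancer, 2 points:** "C00*-C76*, C80*, C81*, C82*, C83*, C84*, C88.3, C88.7, C88.9, C96*, C90.1, C91*-C95*, C81*, C82*, C83*, C84*, C85*, C86*, C88".
- **Cancer, 6 points (metastatic):** "C77*, C78*, C79*, C80".

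The eligibility lists draw the lines elsewhere. Section 9.2.2.1 admits patients in both cohorts on, among other codes, "F45.4*, G62*, or E10.4*-E14.4 plus G63.3". Table 9-2 labels the E10.4-E14.4 range "Diabetes mellitus with neurological complications". Table 9-3 (section 9.2.2.2) defines malignant neoplasms as C00-C97 and excludes a patient only if a listed treatment code falls in the same quarter. The sensitivity analysis in section 9.8.2 removes patients with any C00-C96 diagnosis before the index date.

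**The concern.** Eligibility and risk adjustment treat the same diagnosis differently. A patient can enter the study because of diabetic polyneuropathy and then be scored as having no diabetes. A patient with a malignancy under Table 9-3 can stay in the main analysis and be scored as having no cancer.

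The Cox covariates in section 9.3.2 are sex, age, CCI, treatment duration, quarter of index treatment and the propensity score, with dosage as a time-varying term. The CCI is the only term that measures comorbidity directly. Errors in it weaken adjustment for illness severity in the primary mortality comparison. They also bear on the question in section 8.1 of which comorbidities predict death. Diabetic polyneuropathy is a named subgroup (sections 9.7 and 9.8.1), so patients within one subgroup would get different scores for the same complication.

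**Working it through.** There is no stated figure to reproduce. The check expands the code lists of Table 9-4 and compares them with the ranges in Tables 9-2 and 9-3.

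**1. Diabetes against the inclusion list.** Inputs: the two diabetes rows of Table 9-4, and the range E10.4-E14.4 from Table 9-2. The table's label refers to neurological complications, so the natural reading is the .4 code of each category:

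| Code | Points in Table 9-4 |
|---|---|
| E10.4 | 2 |
| E11.4 | 2 |
| E12.4 | 0 |
| E13.4 | 2 |
| E14.4 | 2 |

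One of five categories admitted as diabetes with a neurological complication scores zero. Table 9-4 lists six digit sets (.9, .1, .2, .3, .4, .5), and each runs E10, E11, E13, E14. E12 is absent from all six, so a character lost in text extraction does not explain it.

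**2. Diabetes within Table 9-4.** Of the 5 × 10 = 50 positions E10.0 to E14.9, those scoring zero are the ten under E12 plus digits .0, .6, .7 and .8 of the other four categories: 10 + 4 × 4 = 26. These 16 non-E12 positions conflict with the inclusion list only to the extent that its range is read as every code from E10.4 through E14.4. That reading spans 6 + 10 + 10 + 10 + 5 = 41 codes, of which 3 + 4 + 10 + 4 + 1 = 22 score zero. It does not fit the label in Table 9-2, so these digits count here as a gap in the table only.

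**3. Cancer against the exclusion list.** The two cancer rows together cover C00-C86, C88, C91-C96 and, within C90, only C90.1 ("C96*, C90.1, C91*-C95"). Against C00-C97 the uncovered codes are C90 other than C90.1, and C97. The numbers C87 and C89 are also uncovered, but the documents do not show whether they are in use.

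**4. Shortfall per patient.** If Table 9-4 matched the eligibility ranges:

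- E12.4 would move from 0 to 2: shortfall 2 − 0 = 2.
- C90 other than C90.1, and C97, would move from 0 to 2: shortfall 2 − 0 = 2.
- A patient who already has a code giving the full points for that condition loses nothing.
- A patient with E12.4 and also an uncomplicated code such as E11.9 would lose 2 − 1 = 1, assuming the higher level counts.

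**5. Who is affected.** For diabetes: patients whose diabetes is recorded only under unlisted codes. For cancer: patients with C90 other than C90.1, or C97, with no other scoring cancer code and no listed treatment code in the same quarter. The protocol gives no code frequencies, so these groups cannot be sized.

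**The case against.** The strongest counter-argument is that the CCI is taken from published modified indices, and a published index need not use the same code list as an eligibility criterion. The regular E10, E11, E13, E14 pattern fits a list taken over whole as well as it fits a slip. This stands in part: whether the index itself omits these codes cannot be settled from the protocol, and the correction has to be checked against it. But the protocol declares no departure from its own definitions. The 2-point cancer row also looks like two lists joined without reconciliation, since C81* to C84* appear twice and C88.3, C88.7 and C88.9 precede C88*.

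Three further points stand. The propensity score includes comorbidities beyond sleep apnoea and depression through an appendix not shown here, is used for matching and enters the Cox model, so it may already capture diabetes or cancer. The baseline period runs from January 2012 to an index date in 2013 or later, so a listed code may well be recorded alongside an unlisted one. The sensitivity analysis removes every patient with C90 before index and leaves only those with C97 alone.

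A reader might infer from 26 of 50 positions (52%) that about half of diabetic patients are mis-scored. The documents do not support that: counting positions weights rare and common codes equally, and any assumed share of patients carrying only unlisted codes would merely restate itself as the result. A reader might also infer that the hazard ratio is biased in a known direction. The same table applies to both cohorts, and nothing shows that the unlisted codes are more frequent in one of them.

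**Conclusion.** The point holds in a limited form. As written, Table 9-4 contradicts the protocol's own lists for E12.4, for C90 other than C90.1, and for C97. A patient with no other scoring code in the row is 2 points too low on the CCI, so this covariate of the mortality Cox model is mismeasured. The missing fourth digits .0, .6, .7 and .8 are an unexplained gap within the table and not a demonstrated conflict with the inclusion list.

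This rests on literal programming of Table 9-4 and on reading the E10.4-E14.4 range as the .4 codes. The number of patients and the size and direction of any bias in the treatment hazard ratio are undetermined. Nothing suggests that the study's conclusions turn on this. It is worth correcting because the protocol fixes the scoring rule itself and a programmer would follow it.

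**What to change.** Before programming, reconcile the diabetes and cancer rows of Table 9-4 with Tables 9-2 and 9-3 and with the code list of the cited modified index:

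- Add E12 in parallel with E10, E11, E13 and E14, with E12.4 in the complicated row.
- Add the rest of C90, and C97, to the 2-point cancer row.
- Assign fourth digits .0, .6, .7 and .8 as the cited index does, without devising a new rule.
- State the reason for any code left out on purpose.

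The listing of C80* in both cancer rows is a separate matter, but it can be resolved in the same edit. The cost is a correction to the diabetes and cancer rows and the matching program lines. No new data are needed.
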